Koy Protocol Contributoro	[name]
Key Protocol Contributors	[name]
	Clinical Associate Professor in Children, Young People &
	Families Nursing; NIHR ICA Clinical Lecturer.
	Nottingham University Hospitals NHS Trust; School of Health Sciences
	[contact]
	[name]
	[name]
	[name]
	Professor of Healthcare Economics
	Division of Rehabilitation and Ageing
	[name]
	University of Nottingham
	[contact]
	[name]
	[name]

	Consultant in Paediatric Orthopaedic Surgery Nottingham University Hospitals NHS Trust Nottingham Children's Hospital [contact] [name]
	[name] Dean and Head of School of Medicine, Faculty of Medicine & Health Sciences University of Nottingham [contact] [name]
	[name] PPI representative
Study Statistician	[name] Associate Professor of Medical Statistics Nottingham Clinical Trials Unit [contact] [name]

STUDY SUMMARY

Study Title	Management of ANkle fractures in CHildren: the feasibility Of a Randomised controlled trial		
Internal ref. no. (or short title)	ANCHOR: Ankle fractures in children		
Study Design	Parallel group, 3-arm, multicentre, feasibility, randomised trial		
Planned Size of Sample (if applicable)	126 in trial 24 parent-child dyads in interviews (18 dyads who were randomised and 6 dyads who declined to participate in the main trial)		
	A total 174 participants will be recruited Inclusion criteria		
Eligibility criteria	 Children (aged 5-15 years inclusive) will be suitable for inclusion in the study if they have either: A proven low-risk ankle fracture on x-ray minimally displaced or undisplaced fibular fracture A clinical undisplaced fracture which fulfils the Ottawa criteria: A history of trauma Tenderness at the posterior edge of the lateral malleolus Unable to weight bear for more than 4 steps No alternative cause of pain identified on x-ray Exclusion criteria Children will be excluded if The injury is more than 7 days old at randomisation They in conjunction with their parents are unable to 		
	 complete the outcome measures chosen in English The child is on the Child Protection Register or where there is any concern about the cause of the injury. 		
Follow up duration (if applicable)	12 weeks		
Planned Study Period	Time from first recruitment to final follow up: 28 months (1/10/2020 – 1/02/2023)		
Research Question/Aim(s)	To establish the feasibility of performing a randomised trial to identify the best treatment for low-risk ankle fractures in children		
Outcome Measures	Electronic, web-based randomisation. Assessors blinded but participants cannot be blinded.		
Statistical Methods	Feasibility of randomised trial including patient feasibility, outcomes feasibility and site and clinician feasibility		

ABBREVIATIONS

- AE Adverse Event
- CI Chief Investigator overall
- CRF Case Report Form
- DMC Data Monitoring Committee
- GCP Good Clinical Practice
- ICF Informed Consent Form
- NHS National Health Service
- P/GIS Parent / Guardian Information Sheet
- PI Principal Investigator at a local centre
- PIS Participant Information Sheet
- REC Research Ethics Committee
- R&D Research and Development department
- SAE Serious Adverse Event

FUNDING AND SUPPORT IN KIND

FUNDER(S) (Names and contact details of ALL organisations providing funding and/or support in kind for this study)	FINANCIAL AND NON FINANCIALSUPPORT GIVEN
National Institute for Health Research Research For Patient Benefit	Full funding for this study

ROLE OF STUDY SPONSOR AND FUNDER

Nottingham University Hospitals NHS Trust are the sponsor for this study. This study is funded by the National Institute for Health Research (NIHR) Research For Patient Benefit (project reference NIHR200580). The views expressed are those of the author(s) and not necessarily those of the NIHR or the Department of Health and Social Care.

The study sponsor will monitor the study conduct against nationally agreed standards. The study sponsor and study funder will have no role in the design, data analysis, interpretation, manuscript writing and dissemination of the results. The sponsor and funders will be consulted for the final decision/s regarding any aspects of this study. The Sponsor reserves the right to discontinue this trial at any time for failure to meet expected enrolment goals, for safety or any other administrative reasons. The Sponsor shall take advice from the Trial Steering Committee and Data Monitoring Committee as appropriate in making this decision.

ROLES AND RESPONSIBILITIES OF STUDY MANAGEMENT COMMITTEES/GROUPS & INDIVIDUALS

Study Steering Groups

The Chief Investigator has overall responsibility for the study and shall oversee all study management. The Chief Investigator will provide supervision for students involved in the research.

The trial management group will meet every 4 weeks to review study progress, any AEs and review study analysis. The trial management group will include the Chief investigator, the deputy chief investigator, qualitative expert and clinical expert

The trial steering committee will meet every 6 months to review progress against the primary endpoints during the study and review all adverse events. This will be composed of the Chief investigator, deputy chief investigator and all co-applicants, including PPI representative.

The data management committee will meet every 6 months ahead of the trial steering committee to review data returns from all sites and monitor key targets such as recruitment and missing data. This will compromise of the study coordinator and study statistician.

Key Words

Fractures, Bone; Child; Ankle; Randomized Controlled Trial; Casts, Surgical; Splints

Contents

SIGNATURE PAGE	
KEY STUDY CONTACTS	3
STUDY SUMMARY	5
ABBREVIATIONS	
FUNDING AND SUPPORT IN KIND	
ROLE OF STUDY SPONSOR AND FUNDER	
ROLES AND RESPONSIBILITIES OF STUDY MANAGEMENT COMMITTEES/GR	
KEY WORDS	7
STUDY FLOW CHART	11

1. BACKGROUND

1.1. SCALE OF THE PROBLEM

Epidemiology of childhood fractures: Incidence and prevalence

There are 12.47 Million children aged 0-16 living in the United Kingdom[1]. A third of these children will sustain a fracture by their 17th birthday[2]. Many of these children will be treated in the community, with 55,000 children requiring a hospital admission to U.K. hospitals each year for fractures[3].

In epidemiological studies from Europe and the United States, the annual incidence of fractures in children is reported to be 20.1-36.1 per 1,000 children. Within these studies, there is discrepancy with the upper limit of 'childhood', ranging from 14-19 years of age. Despite this, the distribution of bone fractures is similar from Germany, Scotland, Sweden, USA and Wales with ankle fractures forming 4-7% of all childhood fractures.

Outcomes following childhood injuries

The impact on recovery and quality of life of injuries and fractures has been evaluated in the U.K. Burden of injury survey. This was a longitudinal survey of 298 children (164 who completed 12-month questionnaires) who attended the Emergency departments of 4 U.K. hospitals that covered a catchment generally representative of the overall U.K. population.

The survey identified that 9% of children who attended the emergency department did not make a full recovery at 12 months on a self-reported questionnaire. Children with a 'mild' injury had a higher chance of making a full recovery[4].

The findings from this survey were replicated in British Colombia, Canada where children who attended the Emergency Department with an injury were surveyed at one year. A significant decrease in quality of life as measured by a decrease of more than 1 standard deviation from baseline PedsQL score was observed for 8% of injured children, independent of injury severity[5].

While these surveys are useful for gaining an understanding of the overall trends of recovery following injury, it remains unclear as to why a significant proportion do not make a full recovery from their injuries. In addition, the World Health Organisation have observed that there are additional impacts to families with children with broken bones including loss of work, schooling and participation with play, parents and peers[6], however there is little published work to evaluate these broader outcomes or to identify if these are relevant to families and clinicians when deciding on treatment strategies.

1.2. CURRENT STATE OF THE EVIDENCE TO MANAGE CHILDHOOD FRACTURES

Cochrane reviews

There are six Cochrane reviews that have evaluated the literature supporting the management of childhood fractures[7]–[12]. These are summarised in Table 1. The reviews have identified 45 trials with sufficient quality to inform practice, with most trials relating to the management of wrist fractures.

The review of interventions for the management of ankle fractures was published in 2016, with searches completed in September 2015. In this review, a higher functional score was identified in children treated with brace or bandage when compared to children treated in a plaster cast.

CONFIDENTIAL ANCHOR Trial Protocol v3.2 28.02.22 IRAS ID 277534 page 12 of 33 FUNDED BY NIHR National Institute for Health Research

Despite this evidence that was available at the time of the Cochrane review, only 22% of 558 American paediatric orthopaedic surgeons report using a removable splint in routine practice for lowrisk ankle fractures (distal fibular avulsion fractures)[13].

The current clinical practice for managing ankle fractures in children is unclear, despite the suggestion that functional treatments may be superior to cast treatments. This uncertainty has led to the development of the research question for this study.

Authors	Year	Торіс	Number of trials	Conclusions
Abraham et al[7]	2011	Surgery for forearm fractures	0	Lack of RCT evidence to inform if surgery is required
Madhuri et al[8]	2013	Conservative techniques for treating forearm fractures	0	Lack of RCT evidence to identify best treatment
Handoll et al[9]	2018	Wrist fractures	30	Low quality RCT evidence. Evidence for good outcome following any treatment for buckle fractures
Capstick & Giele[10]	2014	Fingertip injuries	2	Lack of RCT evidence to identify best treatment
Yeung et al[11]	2016	Stable ankle fracture	3	Low quality evidence of improved recovery with an ankle brace vs plaster
Madhuri et al[12]	2014	Femur	10	Insufficient long-term evidence to compare surgery and traction. Nails may reduce recovery time.

Table 1 Cochrane reviews for childhood fractures

What is a low-risk ankle fracture?

A low-risk ankle fracture is a break to the ankle joint where the patient can safely weight bear. Low-risk fractures include a variety of injuries; avulsion fractures, undisplaced fractures and fractures that cannot be seen on x-ray (**Error! Reference source not found.**). Fractures in children behave differently to those in adults due to their thick periosteum that provides additional stability.

Diagnosis of these injuries can be challenging as occult or growth plate injuries can be very subtle on x-ray images. The Ottawa ankle rules provide a basis for risk stratification of ankle injuries[14], with a sensitivity of 97.9 and specificity of 21% for diagnosis of fracture[15].

Low-risk undisplaced fracture INCLUDE

Low-risk fibula tip avulsion INCLUDE

Low-risk occult fracture (normal x-ray) INCLUDE

Figure 1 Types of ankle fractures categorised as high-risk and low-risk [25]

CONFIDENTIAL ANCHOR Trial Protocol v3.2 28.02.22 IRAS ID 277534 page 13 of 33
FUNDED BY
NIHR National Institute
for Health Research

The Ottawa ankle rule includes:

- A history of trauma
- Tenderness at the posterior edge of the lateral malleolus
- Unable to weight bear for more than 4 steps
- o No alternative cause of pain identified on x-ray

What are the treatment options?

Treatment options for these injuries can be regarded as mobile (where the ankle joint is free to move) or rigid (where the ankle joint is fixed). Techniques to achieve this that have been reported in previous trials are summarised in Table 2:

	Potential advantages	Potential harms
Tubigrip, elasticated bandage[16], [17]	Early movement of the ankle	Some families think it would be less protective*
Removable brace or splint (e.g. Air- stirrup brace)[18], [19]	Early motion with some protection Can be removed for bathing	Higher number of pressure related complications than cast[19]
Below knee cast[16]–[18]	Likely most protective*	No movement at ankle joint, cannot be removed, may result in bone thinning

Table 2 Interventions reported in previous trials. *PPI workshop views

Which is the best treatment?

In a recent systematic review, children prescribed removable treatments have a more rapid return to activities, have a higher functional outcome at four weeks and do not seem to suffer any additional pain[20].

However, there were some significant issues when completing this analysis. There was heterogeneity in study design and conduct. The biggest issue is that all the trials used a different primary outcome measure, with inconsistent reporting of secondary outcomes and statistical techniques. Two studies used variations on the Activity Scale for Kids score (ASK-P) which evaluates function over the preceding two weeks. It would therefore be expected, that if a child remains in a cast then their ASK-p score will be lower as it is difficult to mobilise in a cast even as a healthy volunteer[21].

2. RATIONALE

In order to understand what the ideal treatment for childhood ankle fractures is, we need to establish

- 1. Is it feasible to conduct a randomised trial in the U.K. to answer this question?
- 2. What are the most important outcomes to measure and contrast treatments?
- 3. What is the validity of the instruments available to measure these outcomes?

Work is in progress to identify the outcome domains for a core outcome set in childhood fractures. In a recent systematic review, no patient reported outcome measures have been designed explicitly for childhood fractures, and the quality of evidence available to assess measurement properties is poor.

The ANCHOR study will address these uncertainties with a feasibility randomised trial to provide feasibility data and additional validation of outcome measures.

3. RESEARCH QUESTION AND AIMS

3.1. TRIAL PURPOSE

To establish the feasibility of performing a randomised trial to identify the best treatment for low-risk ankle fractures in school aged children

Objectives

Evaluation of the feasibility of a definitive randomised trial through:

- 1. Patient feasibility
 - a. Compliance with treatment and other outcome scores
 - b. Are there any complications with treatments?
- 2. Outcome feasibility
 - a. Determine the ideal outcome measure for this trial.
 - b. Determine the effect sizes of the interventions for a sample size calculation of a definitive trial
- 3. Site and clinician feasibility
 - a. Numbers of eligible patients
 - b. Recruitment and retention rates for this trial
 - c. Fidelity assessment of inclusion criteria and interventions

3.2. OUTCOMES

Feasibility outcomes

Feasibility outcomes will determine if a future main trial is possible and desirable. The following feasibility outcomes will be assessed:

- Recruitment rates compared to site screening logs;
- Retention rates, drop out and crossovers;
- Adherence to treatments through a 14-day patient diary;
- Trial experience and qualitative feedback from participants.

Clinical outcomes

Clinical outcomes will be collected to assess the relevance and acceptability of these outcomes for use in a future definitive RCT and to validate the tools to measure outcomes for childhood fractures through:

- 1. Calculation of minimally important clinical difference for outcome tools;
- 2. Validation of PROMIS Mobility for ankle fractures in children.

The following clinical outcomes will be assessed:

- Physical function as measured by PROMIS Mobility;
- Quality of life as measured by EQ-5D-Y;
- Global rating of change score;

- Daily pain scores through a 14-day patient diary;
- Re-injury rates;
- Complications.

Safety endpoints

No significant safety issues are expected related to this trial. Spontaneous adverse events will be monitored during the trial, in particular at the 6-week follow up requiring additional treatment or physiotherapy.

Stopping rules and discontinuation

No specific stopping or discontinuation rules have been identified for this study. As this is a feasibility study, if the accumulating evidence shows that the study is not feasible then at the advice of the TSC, the sponsor reserves the right to stop the study at any time

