3.4. PROGRESSION CRITERIA

The trial will progress to a full trial if all the following are fulfilled:

- 1. A suitable outcome measure can be determined using the feasibility data and the effect size of the three interventions estimated along with the standard deviations in order to properly power a definitive trial;
- 2. None of the interventions have an unacceptable complication rate as agreed by the trial steering committee;
- 3. Recruitment rates are greater than 50% anticipated allowing a full trial to be completed within a 3-year time frame within the U.K. Trauma Trials Network;
- 4. Study retention is greater than 60% at the 6-week follow up in all groups;
- 5. The effect size and standard deviation produces a sample size calculation that can be achieved across the trauma trials network within a reasonable time frame and within scope of an NIHR HTA funding;

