4.4. STATISTICS

Feasibility outcomes

All analyses will be documented in a Statistical Analysis Plan which will be finalised prior to database lock. Descriptive statistics (with 95% confidence intervals (CI) where appropriate) will address feasibility objectives (e.g. recruitment and follow-up rates, missing clinical outcome data, intervention adherence, standard deviations for clinical outcomes). Demographic and baseline clinical characteristics will be descriptively compared by study arm.

Assessment of efficacy

As this is a feasibility study, no formal assessment of efficacy will be undertaken. The potential primary clinical outcome for the future main trial will be analysed descriptively per arm, with confidence intervals generated using appropriate regression model to estimate the likely range of intervention effects. Secondary clinical outcomes will be descriptively summarised by treatment arm.

There is no consensus yet on the outcomes that should be measured in childhood fractures. In our preparatory work for this proposal families have identified 'return to normal activities' and 'pain' as the two most important outcomes.

Initial findings from the CORE-KIDS lower limb fracture study have suggested that the EQ-5D-Y and PROMIS Mobility outcome sets should be used as the primary outcome measures, as they assess a broad range of function and mobility domains.

A formal minimally important clinical difference (MCID) in this patient group has not been calculated, and previous trialists have used a range between 5 and 7%^{9,10} to represent an important difference.

Assessment of safety

No significant safety issues are expected related to this trial. Spontaneous adverse events will be monitored during the trial, in particular at the 6-week follow up requiring additional treatment or physiotherapy.

All adverse events will be discussed at the trial management group meetings. Significant adverse events will be escalated to the trial steering committee and study sponsor.

Procedures for missing, unused and spurious data

Proportions and patterns of missing data will be summarised by arm but there will be no imputation for missing data at follow-up assessments nor any model-based adjustment for missing data.

Baseline and outcome data will be summarised by allocated group, regardless of adherence with the intervention. Safety will be evaluated using the Safety set: All randomised participants who receive at least one treatment.

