5.1. STUDY ACTIVITIES FOR THE TRIAL

At time of diagnosis (typically in the Emergency Department), potential participants may be identified and provided with a patient information sheet by the usual care team. Screening of participants may also be performed by the usual care team in face-to-face or virtual fracture clinics and information sheets provided.

CONFIDENTIAL ANCHOR Trial Protocol v3.2 28.02.22 IRAS ID 277534 page 19 of 33
FUNDED BY
NIHR National Institute
for Health Research

Where eligible participants wish to join the study, a member of the research team will obtain informed consent and undertake randomisation to a product at the point in the local care pathway where a definitive treatment is being offered. This may be in the Emergency Department, Emergency clinics or fracture clinic depending on the local pathways.

Following completion of pre-injury baseline scores and CRF, the patient will be randomised using a web-based electronic randomisation with 1:1:1 allocation with stratification for fracture type (occult and visible fracture line) and child age (5-10, 11-15) with block sizes of 3, 6 & 9.

Treatment will be provided according to random allocation by a trained member of the clinic staff according to the manufacturer's guidelines. As described in section 4.2, the available treatments are:

- 1. Supportive bandage.
- 2. Semi-rigid, removable brace (including splints or custom orthoses).
- 3. Below knee walking cast

Routine follow up will be provided according to local protocols and decided by the usual care team. Patients who have a below knee walking cast are likely to require a clinic review to remove the device. Other patients may be discharged with instructions to remove their own device at home.

A patient diary is provided to participants at time treatment is provided. The diary is returned after two weeks.

Outcome assessment will be completed by the central research team using an electronic interface through the Redcap system. Outcomes will be collected at 2 weeks, 6 weeks and 12 weeks. Telephone, SMS text messages (Esendex, Nottingham) and e-mail reminders will be used to encourage completion of outcome scores.

	Baseline (pre- injury) score	Review 1 (Day 7-23)	Review 2 (Day 35-52)	Review 3 (Day 84-100)
Demographics	Х			
Physical function (PROMIS Mobility)	х	х	Х	Х
Quality of life (EQ-5D-Y)	х	Х	х	Х
Daily pain (faces pain or VAS)	х	Х		
Re-injuries			Х	Х
Complications		Х	Х	Х
Parent satisfaction			Х	Х
Child satisfaction			Х	Х

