7.8. Adverse Event

Potential adverse events

Table 4 lists adverse events reported in previous trials of childhood low-risk ankle fractures.

Children participating in the ANCHOR Trial will be screened at clinical follow up for the following potential adverse events:

- Pressure related issues
 - o Heel pain
 - o Blisters
 - o Sores
- Skin irritation or rashes
- Persistent swelling
- Persistent bruising
- Additional visits to healthcare providers (e.g. physiotherapy, fracture clinic etc)

Table 4 Adverse events reported in previous trials of "low-risk" ankle fractures

Trial	Adverse events	
Boutis et al 2007[18]¤	Unscheduled visits to healthcare provider	
	Skin irritation / rash	
Barnett et al 2012[19]	Additional visits to healthcare provider	
	Pressure related complications	
Gleeson et al 1996[16]	No adverse events reported	
Launay et al 2008[17]	Persistent swelling and bruising	

Reporting Procedures

Proportionate to the type of study and participant involvement, all adverse events should be reported. Depending on the nature of the event the reporting procedures below should be followed. Any questions concerning adverse event reporting should be directed to the Chief Investigator in the first instance.

Non serious AEs

All such events, whether expected or not, should be recorded.

Serious AEs

An SAE form should be completed and sent to the Chief Investigator within 24 hours. Hospitalisations for elective treatment of a pre-existing condition do not need reporting as SAEs.

All SAEs should be reported to the Derby REC where in the opinion of the Chief Investigator, the event was:

'related', ie resulted from the administration of any of the research procedures; and

'unexpected', ie an event that is not listed in the protocol as an expected occurrence

Reports of related and unexpected SAEs should be submitted within 15 days of the Chief Investigator becoming aware of the event, using the NUH SAE form for non-CTIMP studies.

Local investigators should report any SAEs as required by their Local Research Ethics Committee and/or Research & Development Office.

The Sponsor Contact Details for SAEs are:

- Email ([contact])
- Hand delivered not mailed ([name])
- [contact]) if written report not immediately possible

Any queries please contact a member of staff in the Nottingham University Hospitals Research & Innovations department:

- [contact]
- Email: [contact]

Participant removal from the study due to adverse events

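### Adverse events are described as spontaneous in 3.2 and 4.4 but as checklist-screened at clinical follow-up in 7.8, so complication rates may be collected unequally across arms, and criterion 2 names no source

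*Protocol*

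**What the plan says.** The protocol describes how harms are found in three places.

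- **Sections 3.2 (Safety endpoints) and 4.4 (Assessment of safety)** carry the same sentence: "Spontaneous adverse events will be monitored during the trial, in particular at the 6-week follow up requiring additional treatment or physiotherapy".
- **Section 7.8** says: "Children participating in the ANCHOR Trial will be screened at clinical follow up for the following potential adverse events". The list is pressure-related issues (heel pain, blisters, sores), skin irritation or rashes, persistent swelling, persistent bruising, and additional visits to healthcare providers. On non-serious events it adds: "All such events, whether expected or not, should be recorded".
- **Section 3.2 (Clinical outcomes) and Table 3** list Complications as an outcome, without defining it, and mark it at Reviews 1, 2 and 3. Section 5.1 has the central team collect outcomes electronically: "Outcomes will be collected at 2 weeks, 6 weeks and 12 weeks".

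On who is seen in clinic, section 5.1 says "Patients who have a below knee walking cast are likely to require a clinic review to remove the device", and then "Other patients may be discharged with instructions to remove their own device at home".

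Criterion 2 in section 3.4 reads: "None of the interventions have an unacceptable complication rate as agreed by the trial steering committee". Section 4.4 sets the safety denominator as "All randomised participants who receive at least one treatment".

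**The concern.** Waiting for a family to mention a blister and asking about blisters by name are different ways of collecting data. The second can be expected to find more minor events. The protocol prescribes both and ties the prompted one to a clinic contact that the arms are not equally likely to have.

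Complications of treatment are a stated objective (3.1, objective 1b), and criterion 2 is one of five conditions that must all be met before a full trial. Section 4.2 expects pressure marks and blisters more often with the brace than with the cast. These minor events are the ones most sensitive to prompting, and the brace arm is one of the two that may not return to clinic. If prompting happens mainly in clinic, the brace excess that the protocol anticipates could be understated. An event that nobody asked about cannot be recovered at analysis, so a later analysis plan cannot repair this.

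**Working it through.** The plan states no complication rate, no capture rate and no limit, so there is no figure to reproduce. The check sets the passages side by side and then shows how unequal detection would act.

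**1. The three descriptions**

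| Place | How events are found | Where or when | Arms reached |
|---|---|---|---|
| 3.2 and 4.4 | Spontaneous | During the trial, with emphasis on 6 weeks | All |
| 7.8 | Prompted against a list | Clinical follow-up | Cast likely; bandage and brace perhaps not (5.1) |
| Table 3 | Not stated; item undefined | Reviews 1, 2 and 3, collected centrally | All |

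The first two rows conflict on method. Only the third reaches every arm at fixed times, but it does not say what is asked.

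**2. The link to criterion 2.** It refers to a complication rate without naming any of the three sources, a time window or a limit. A denominator is available from the safety set in 4.4.

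**3. Coverage of the list.** Section 4.2 gives two known side effects: pressure-related injury and plaster saw injury. The 7.8 list contains the first and not the second, which is specific to the cast.

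**4. Sensitivity to detection.** With 42 children per arm (6.2), one child more or fewer changes the rate by 1/42 = 2.4 percentage points.

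Suppose two arms share a true rate p. One records every event and the other records a fraction c. The spurious difference is p − cp = p(1 − c). Both p and c are assumptions, because the documents give neither.

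| Assumed p | c = 0.25 | c = 0.50 | c = 0.75 | c = 1 |
|---|---|---|---|---|
| 10% | 7.5 points | 5.0 | 2.5 | 0 |
| 20% | 15.0 | 10.0 | 5.0 | 0 |
| 30% | 22.5 | 15.0 | 7.5 | 0 |

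For example, with p = 20% and c = 0.50 the expected counts are 42 × 0.20 = 8.4 and 42 × 0.10 = 4.2. At the nearest whole numbers the committee would see 8/42 = 19.0% (exact 95% CI 8.6% to 34.1%) and 4/42 = 9.5% (2.7% to 22.6%), although the arms do not truly differ. The wide intervals describe sampling error only and would not reveal the bias. If the same question is put to every arm, the two arms share one capture fraction and the artefact disappears.

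**The case against.** The best defence is that the descriptions add to one another. Section 7.8 requires all events to be recorded, expected or not, so volunteered and screened events both count. Complications at Reviews 1 to 3 is a natural source for criterion 2 and is collected centrally in every arm. The steering committee reviews all adverse events and is not described as applying a cut-off to one count. Sections 3.3 and 4.4 also mention clinic attendance and a 6-week follow-up, which could suggest that all arms are seen.

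Much of this stands, and it limits the point. It does not remove it. A rule to record everything does not settle whether anyone asks. The central item could serve, but its content is undefined and criterion 2 does not cite it. Section 4.3 has follow-up done remotely, and 5.1 leaves routine clinic follow-up to local protocols.

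Two stronger readings are tempting but unsupported.

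- A reader might infer that 3.2 and 4.4 count only 6-week events needing extra treatment. The words in particular mark an emphasis and exclude nothing. The 7.8 list also includes additional visits such as physiotherapy, so the descriptions overlap.
- A reader might infer that criterion 2 has two rival definitions and that an arm would pass under one and fail under the other. The criterion has no definition. Any pass or fail probability would need an invented limit and invented rates, and a committee could set its limit to suit whichever definition was in use.

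**Conclusion.** The concern holds as a conflict over how events are elicited, combined with a decision criterion that names no source. Spontaneous reporting (3.2 and 4.4) and checklist screening (7.8) cannot both be the method. Because 7.8 places the screening at a contact that cast patients are likelier to have, minor events may be detected unequally by arm.

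The size is unknown. Under the assumed true rates of 10% to 30% and capture of 25% to 75% in the less-prompted arm, the artefact runs from 2.5 to 22.5 percentage points. It is nil if the central reviews already ask the same question of everyone. The direction, with more recorded in the cast arm, rests on the further assumption that prompting follows clinic attendance. The documents do not show that any arm's progression result would change. The passages still need reconciling, because the collection method cannot be corrected after the data are in.

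**What to change.** Reconcile 3.2, 4.4 and 7.8 on one method:

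- One prompted complications checklist, asked in the same words at Table 3 Reviews 1, 2 and 3 in every arm.
- Its content should be the 7.8 items, the known side effects in 4.2 including plaster saw injury, and an any-other item. The 7.8 list alone should not be used, because it would omit a harm specific to the cast while counting brace blisters.
- Volunteered events are also recorded, with a note of how each was found.

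In 3.4, state that criterion 2 uses the per-arm proportion of children with a complication from this source, with the 4.4 safety set as denominator. Report events needing additional treatment or physiotherapy on a separate line, so that the committee sees both. Acceptability can remain the committee's judgement.

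The cost is wording in 3.2, 3.4, 4.4 and 7.8 and a short question set in a review item that is already scheduled. Recorded rates will be somewhat higher than a spontaneous count would give. No change to clinical care or clinic attendance is implied.
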